6.3.2 Statistical Significance Level

All statistical tests will be two-sided and will be performed at the 5% level of significance, unless otherwise stated.

6.3.3 Software

All statistical analyses will be performed using Statistical Analysis Software (SAS[®]) Version 9.2 or later. The PK analysis will be performed using WinNonlin Professional Software Version 6.3.

6.3.4 Missing Data

Any AEs with unknown severity or causality will be considered as ‘severe’ and ‘related’ respectively, for the tabulations. The unknown severity or causality without imputation will be presented in listings.

AEs with missing dates/times will be handled as described below. The incomplete dates/times without imputation will be presented in listings.

Concomitant medications (CMs) with missing times will be handled as described below. The incomplete times without imputation will be presented in listings.

All other data will be analyzed and reported as observed. No imputation schemes for other missing values will be applied.

PAREXEL International
Statistical Analysis Plan

Handling of AEs with Missing Dates/Times

Any AEs with incomplete start and or end dates/times will be handled as described below for the classification as treatment-emergent, assignment to treatment periods and calculation of duration.

- Adverse events with unknown start times, but with start date known, will be imputed with a time of 00:00 hours, unless the start date corresponds to any given dosing date, in this case the start time will be imputed with the time of dosing. If this results in a start date/time after end date/time of the AE then the start time will also be imputed with 00:00 hours.
- Adverse events with completely unknown start dates will be imputed with the date and time of first IMP administration, unless the end date is known and prior to first administration of IMP, then the start date will be imputed as the date of screening and a time of 00:00 hours.
- Adverse events with completely unknown end times, will be imputed with an end time of 23:59 hours;
- Adverse events with completely unknown end dates will be imputed with the date of final FU (or date of discontinuation in the case of withdrawals).

Adverse events with partially known start dates will be treated as follows:

- If only the day is missing, then the day will be imputed with the first day of the month, unless the month and year in which the AE started is a month and year in which IMP was administered, then the day will be imputed with the first day on which IMP was administered in that month. If this results in a start date after end date then the day will be imputed with the first day of the month.
- If both the day and month is missing and the year is a year in which IMP was administered then the day and month will be imputed with the day and month of first IMP administration. If this results in a start date after end date then the day and month will be imputed with 01JAN. If the year is not a year in which IMP was administered then the day and month will also be imputed with 01JAN.
- If only the year is missing then the year will be imputed with the year of first IMP administration.

PAREXEL International

Statistical Analysis Plan

Adverse events with partially known end dates will be treated as follows:

- If only the day is missing, then the day will be imputed with the last day of the month, or date of final FU/early discontinuation if this is earlier.
- If the day and month is missing then the end date will be imputed as 31 December, or date of final FU/early discontinuation if this is earlier.

Handling of CMs with Missing Dates/Times

Any CMs with incomplete start and or end dates/times will be handled as described below for the classification as concomitant medication, assignment to treatment periods and calculation of duration.

- Concomitant medications with unknown start times, but with start date known, will be imputed with a time of 00:00 hours, unless the start date corresponds to any given dosing date, in this case the start time will be imputed with the time of dosing. If this results in a start date/time after end date/time of the CM then the start time will also be imputed with 00:00 hours.
- Concomitant medications with completely unknown start dates will be imputed with the date and time of first IMP administration, unless the end date is known and prior to first administration of IMP, then the start date will be imputed as the date of screening and a time of 00:00 hours.
- Concomitant medications with completely unknown end times will be imputed with an end time of 23:59 hours.
- Concomitant medications with completely unknown end dates will be imputed with the date of final FU (or date of discontinuation in the case of withdrawals).

Concomitant medications with partially known start dates will be treated as follows:

- If only the day is missing, then the day will be imputed with the first day of the month, unless the month and year in which the CM started is a month and year in which IMP was administered, then the day will be imputed with the first day on which IMP was administered in that month. If this results in a start date after end date then the day will be imputed with the first day of the month.

PAREXEL International

Statistical Analysis Plan

- If both the day and month is missing and the year is a year in which IMP was administered then the day and month will be imputed with the day and month of first IMP administration. If this results in a start date after end date then the day and month will be imputed with 01JAN. If the year is not a year in which IMP was administered then the day and month will also be imputed with 01JAN.
- If only the year is missing then the year will be imputed with the year of first IMP administration.

Concomitant medications with partially known end dates will be treated as follows:

- If only the day is missing, then the day will be imputed with the last day of the month, or date of final FU/early discontinuation if this is earlier.
- If the day and month is missing then the end date will be imputed as 31 December, or date of final FU/early discontinuation if this is earlier.

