#### *6.4.1.5 Reporting Serious Adverse Events*

All SAEs that occur during the period of observation, and all SAEs occurring up to 30 days after receiving the last dose of study drug, whether considered to be associated with the study drug or not, must be reported within 24 hours by telephone, fax, or eCRF to the PAREXEL Safety Contact using the numbers in the List of Study Personnel.

SAEs occurring after the end of the study should be reported to the Sponsor/PAREXEL by the Investigator if the Investigator considers there is a causal relationship with the study drug.

The minimum information required for an initial report is:

- Name of person sending the report (i.e., name, address of Investigator);
- Subject identification (screening/randomization number, initials, NOT subject name);
- Protocol number;
- Description of SAE;
- Causality assessment, if possible.

However, as far as possible all points on the SAE form should be covered in the initial report, or the completed SAE form itself must be faxed to the PAREXEL Safety Contact. The original SAE form must then be sent by mail to the PAREXEL Safety Contact. In addition, the event must be documented in the EDC system.

In case the PAREXEL Safety Contact cannot be contacted (e.g., out of normal working hours or at weekends), an automated reporting service is available. The required information should be faxed and a message should be left on the voicemail service (for phone/fax numbers see the numbers in the List of Study Personnel).

After receipt of the initial report, the safety center will review the information and, if necessary, contact the Investigator, to obtain further information for assessment of the event. PAREXEL will be responsible for all information processing and reporting according to local legal requirements. Where necessary, Investigators will inform Regulatory Authorities in their own countries.

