**PAREXEL International**  
**Toll free SAE [contact]-hour service)**  
**SAE [contact]**  
**Email: [Medical\\[contact]](mailto:[contact])**

#### *6.4.1.6 Follow-up of Adverse Events*

All AEs experienced by a subject, irrespective of the suspected causality, will be monitored until the AE has resolved, any abnormal laboratory values have returned to baseline or stabilized at a level acceptable to the PI, until there is a satisfactory explanation for the changes observed, until the subject is lost to follow-up, or until the subject has died.

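### The SAP's rules for missing AE end dates can place the imputed end before a recorded end month, or before onset, because the follow-up/discontinuation cut-off has no consistency check

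*SAP*

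**What the plan says.** SAP 6.3.4 imputes incomplete AE dates "for the classification as treatment-emergent, assignment to treatment periods and calculation of duration". Its end-date rules are:

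- End date wholly unknown: "Adverse events with completely unknown end dates will be imputed with the date of final FU (or date of discontinuation in the case of withdrawals".
- Day missing: the end is "imputed with the last day of the month, or date of final FU/early discontinuation if this is earlier".
- Day and month missing: 31 December, with the same cut-off.

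The start-date rules include a consistency check, for example: "If this results in a start date after end date then the day will be imputed with the first day of the month". The end-date rules have no counterpart. Incomplete dates appear unimputed in the listings.

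The protocol expects events to run past the cut-off. Under 6.4.1.6 all AEs, "irrespective of the suspected causality, will be monitored until the AE has resolved" or until another closing condition is met (stabilised, explained, lost to follow-up, died). Under 6.4.1.5 the site reports "all SAEs occurring up to 30 days after receiving the last dose of study drug". Sections 6.4.1.4 and 6.4.1.5 also take events after study end that the investigator judges related.

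SAP 6.3.15.1 puts duration in days in the AE listing, next to outcome and an ongoing flag.

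**The concern.** The cut-off treats final follow-up or discontinuation as the latest date on which an event with an incomplete end date can have ended. The protocol's collection rules allow events to end, and some to begin, after that date. Applied literally, the SAP rule can then replace a recorded end month with an earlier one, or end an event before it began.

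At stake is how individual events read. Safety is the primary objective, and time of onset and offset belongs to the named safety endpoint. With six active subjects per cohort, an AE in a subject who withdrew will be looked at one by one. Because the listing shows dates as recorded, a reader could see an end in April beside a duration that stops in March.

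**Working it through.** The plan gives no figure on this point, so there is none to reproduce. The end-date rules were applied as written to constructed timelines.

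**Inputs**

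- Final follow-up: Day 14 (±1) in both parts (Protocol Tables 7-1 and 7-2).
- Last planned dose: Day 1 in Part A, Day 7 in Part B.
- SAE window: last dose + 30 days (Protocol 6.4.1.5).
- Assumptions: Day 1 = 20 March 2017 for the calendar examples; duration = end - start + 1, counted inclusively. The SAP gives no duration formula. By simple difference every figure below is one day lower.

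**How far the SAE window runs past final follow-up**

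- Part A: 1 + 30 = Day 31; 31 - 14 = 17 days (16 to 18 with the visit window).
- Part B: 7 + 30 = Day 37; 37 - 14 = 23 days (22 to 24).

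**The rule applied**

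| Case | Imputed end | Imputed duration (days) | Recorded or assumed true duration (days) |
|---|---|---|---|
| 1. Onset 21 March, discontinued 22 March, end recorded as April | earlier of 30 April and 22 March = 22 March | 22 - 21 + 1 = 2 | at least 12 (21 March to 1 April) |
| 2. As case 1, but onset 31 March | 22 March | 22 - 31 + 1 = -8 | at least 2 (31 March to 1 April) |
| 3. Part B, last dose and discontinuation Day 3 (SAE window to Day 33), SAE onset Day 20, end unknown | Day 3 | 3 - 20 + 1 = -16 | at least 1 |
| 4. Completer, final follow-up Day 14, SAE onset Day 20, end unknown | Day 14 | 14 - 20 + 1 = -5 | at least 1 |
| 5. Onset Day 2, discontinued Day 3, truly ended Day 10 but recorded as unknown | Day 3 | 3 - 2 + 1 = 2 | 10 - 2 + 1 = 9 |
| 6. Onset and true end Day 2, discontinued Day 3, end recorded as unknown | Day 3 | 3 - 2 + 1 = 2 | 2 - 2 + 1 = 1 |

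Case 1 overwrites recorded information. Cases 2 to 4 end before they start. Cases 5 and 6 show that the error can go either way.

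The start-date check does not rescue cases 2 to 4. It moves only a start that was itself imputed, and here the onset is recorded in full.

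**What is not touched.** An event with a complete end date keeps it. In a dosed subject the cut-off cannot fall before the first dose, so cutting an end date back does not change treatment-emergent status. The AE tables by system organ class, preferred term, severity and relationship do not use the end date, and the SAP's table list has no summary of AE duration.

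**Two related gaps.** The SAP does not define the date of discontinuation. The disposition listing in 6.3.8 carries last drug administration, completion or early termination, and final contact, any of which could be meant. And SAP 6.1.2.1 sets an unknown end time to 00:00, whereas 6.3.4 sets it to 23:59. The first can itself put the end before the start for an event that began and ended on the same day.

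**The case against.** The strongest reply is that this will rarely arise and would be visible if it did. Following AEs to resolution makes a missing end date less likely. AE reports should carry the date and time of resolution, data queries chase gaps, and this is one centre with subjects confined during dosing. For partial dates discontinuation is only a cap, used when it falls before the end of the recorded month or year. A negative duration needs both an onset after the cut-off and a missing or partial end date. The listing also shows the raw dates, the outcome and the ongoing flag.

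All of that stands, and it limits the size of the point. The documents give no frequency and none can be derived. It does not make the rule correct where it applies: a stated rule that overrides a recorded month or yields a negative duration gives a wrong value.

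A reader might infer that the rule systematically makes the AEs of withdrawn subjects look short, and more so the earlier they stopped. The documents support neither part. Most of the defaults are late ones (month end, 31 December, final follow-up), and case 6 shows an event lengthened. The shortfall in case 5 is the true end minus the cut-off date, and nothing ties its size to how early a subject stopped. How near the cut-off lies to onset also depends on which date counts as discontinuation, which is undefined.

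**Conclusion.** The point holds as a minor error in a stated rule. For an AE or SAE with a missing or partial end date, SAP 6.3.4 can contradict a recorded end month (2 days against at least 12), give a negative duration (-16 days after withdrawal, -5 days in a completer), cut short an event unresolved at discontinuation, or lengthen one that had already ended. Completers are exposed as well as withdrawn subjects, because the SAE window runs about 17 days (Part A) or 23 days (Part B) past final follow-up.

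The figures rest on constructed timelines, inclusive day counts and a literal reading of the rule. Only the duration field of the AE listing is affected. A reader might infer that the safety tables or dose escalation are at risk; the documents do not support that, since neither depends on an imputed end date.

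**What to change.** Amend SAP 6.3.4 as follows.

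1. An imputed end date may not precede the start of the AE.
2. Apply the follow-up/discontinuation cap to a partial end date only when the cap date is not earlier than the start of the recorded month or year. Otherwise use the last day of the recorded period. Case 1 then ends on 30 April: 11 + 30 = 41 days, the upper end of what the record allows (12 to 41).
3. For an AE that is ongoing or has a wholly unknown end date, impute no end date. Flag it as ongoing or unknown and leave duration missing, or show it as at least the time to final contact, a date already in the 6.3.8 listing. In case 3 with final contact on Day 33, that is at least 33 - 20 + 1 = 14 days. Leaving duration missing matches SAP 6.3.10, which calculates none for concomitant medications lacking a start or end date.
4. State which date in the 6.3.8 listing is the date of discontinuation.
5. Use one rule for unknown end times in 6.1.2.1 and 6.3.4.

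The cost is SAP wording and a few lines of programming before database lock. No new data are needed.

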6.3.5 Interim Analysis

No formal interim analysis is planned.

6.3.6 Protocol Deviations

Major protocol deviations will be defined at the data review meeting (DRM). Subjects with major protocol deviations might be excluded from the Pharmacokinetic population.

All protocol deviations will be recorded by the Investigator and will be listed by subject with each study part, by cohort. All protocol deviations will be discussed between PAREXEL and the Sponsor during the data review meeting before database lock in order to determine whether these may warrant exclusion of a subject from the statistical analyses.

Protocol deviations will be presented using the safety population.

All protocol deviations will be listed [Listing 16.2.2.1 (Part A) and Listing 16.2.2.2 (Part B)] by study part and cohort will include, the subject number, actual study day (if applicable), visit, time point, date/time, and a description of the deviation and classification (major or minor).

PAREXEL International Statistical Analysis Plan

Protocol deviations will be summarized [Table 14.1.3.1 (Part A) and Table 14.1.3.2 (Part B)] by treatment period for each study part for the subjects in the safety population.

Major protocol deviations will include the following:

- Deviation from the inclusion and exclusion criteria
- Deviation from study medication compliance in terms of medical conditions and/or AEs that may have interfered with drug absorption or with respect to factors likely to affect the primary endpoints
- Deviation from study procedure compliance; Non-compliance to study procedures or deviations from study procedures likely to affect the primary endpoints.

Time window deviations for PK blood sampling and safety or exploratory assessments will also be listed as protocol deviations. Tolerance windows for safety, PK blood sampling and exploratory assessments (when applicable) are provided in the final Windows Allowance Agreement (WAA).

6.3.7 Demographic Data

All demographic data will be listed and summarized using the safety population.

Demographic characteristics will be tabulated [Table 14.1.2.1 (Part A) and Table 14.1.2.2 (Part B)] within each study part, and by cohort (n, mean, standard deviation, minimum and maximum for age, height, weight and BMI; and frequency counts and percentages for sex, race and ethnicity).

Demographic characteristics will be listed [Listing 16.2.4.1.1 (Part A) and Listing 16.2.4.1.2 (Part B)] by subject within each study part, and by cohort and will include subject number, age (years), gender, race, ethnicity, height (cm), weight (kg) and BMI (kg/m^2).

Informed consent [Listing 16.2.1.2.1 (Part A) and Listing 16.2.1.2.2 (Part B)], study visits [Listing 16.2.1.3.1 (Part A) and Listing 16.2.1.3.1 (Part B)], Failed Inclusion and exclusion criteria will be listed [Listing 16.2.1.4.1 (Part A) Listing 16.2.1.4.2 (Part B)] and Assignment to Analysis Populations [Listing 16.2.3.1 (Part A) and Listing 16.2.3.2 (Part A)].

PAREXEL International
Statistical Analysis Plan

6.3.8 Subject Disposition

Subject disposition will be tabulated [Table 14.1.1.1 (Part A) and Table 14.1.1.2 (Part B)] within each study part, and by cohort including number and percentage of dosed, withdrawn and completed subjects and primary reason for discontinuation.

Subject disposition will be listed [16.2.1.1.1 (Part A) and Listing 16.2.1.1.2 (Part B)] within each study part, and by cohort and will include the following information: Subject Number, Primary Reason for Withdrawal, AE number, Date of Last Drug Administration, Date of Completion/Early termination, Date of Final Contact with subject, Subject status at the time of completion, Blind Broken (Yes/No), Date/Time of Blind and Reason Broken Blind.

Subject disposition will be summarized for each treatment and overall including the number of subjects randomised, number and percentage of subjects dosed, number and percentage of discontinued subjects and primary reason for discontinuation* [Table 14.1.1.1 (Part A) and Table 14.1.1.2 (Part B)]. This will be done for subjects in the safety population.

*The primary reason for discontinuation will be documented as one of the following:

- ECG abnormalities (any increases in QTcF > 500 msec or increase > 60 msec from baseline as confirmed with 3 consecutive ECGs taken within 5 minutes, with at least a 1-minute interval)
- Suicidality (any suicide attempt or any recent suicidal ideation (a level of 4 or 5) since the last assessment, or a significant risk to commit suicide, as judged by the PI using the CSSRS)
- Liver Safety monitoring
- After enrollment, the subject is found to violate the inclusion/or exclusion criteria
- Adverse event
- Subject lost to follow-up
- Major protocol violation
- Use of prohibited medications
- Any serious safety concern
- Premature termination of the study

PAREXEL International
Statistical Analysis Plan

- Death
- Other

6.3.9 Medical History

Medical history will be coded using Version 19.1 of the Medical Dictionary for Regulatory Activities (MedDRA).

Medical history will be summarized [Table 14.1.4.1 (Part A) and Table 14.1.4.2 (Part B)] by overall within study part by cohort using safety population.

Medical history will be listed [Listing 16.2.4.2.1 (Part A) and Listing 16.2.4.2.2 (Part B)] by study part, and will include subject Number, Medical History Number, Description of Disease/Procedure, MedDRA Preferred Term, MedDRA System Organ Class, Start Date/Study day, Stop Date, Status, Medication Taken, and Concomitant medication number.

6.3.10 Concomitant Medication

Prior and concomitant medication will be coded according to the latest available version of the World Health Organization's Drug Dictionary (WHO-DD) and the Anatomical Therapeutic Chemical (ATC) classification system.

Summary tables will be provided for prior medications and significant nondrug therapies significant nondrug therapies within each study part, and by cohort [Table 14.1.5.1 (Part A) and Table 14.1.5.2 (Part B)] for the safety population. Summary tables will be provided for concomitant medications and significant nondrug therapies within each study part, and by cohort [Table 14.1.6.1 (Part A) and Table 14.1.6.2 (Part B)] for the safety population.

Prior and concomitant medication will be listed [Listing 16.2.4.3.1 (Part A) and Listing 16.2.4.3.2 (Part B)] by subject within each study part, by cohort, and will include, at least, the following information: Product/s (study drug), medication/generic name (trade name), dose (and dose units), frequency, route of administration, start date/study day, end date/end date, duration, indication and origin (medical history or AE). Duration of concomitant medication will be calculated and included in the listing. The duration of prior or concomitant medications will be calculated based on the start and end dates. Duration of medication administration will not be calculated for concomitant medications with start date and/ or end date missed.

PAREXEL International
Statistical Analysis Plan

